Specific Aim 1. We will recruit 15 runners; ten with unilateral and five with bilateral transtibial amputations that currently use and have at least one year of experience with distance-running RSPs. Subjects will be between 18-55 years old and have no current problems with their prosthesis or residual limb. There will be no restrictions on sex, race, or ethnicity for inclusion. Subjects will be at a K4 Medicare Functional Classification Level, which is defined as a person who has the ability or potential for prosthetic ambulation that exceeds basic ambulation skills, exhibiting high impact, stress, or energy levels. Subjects will have no known cardiovascular, pulmonary, or neurological disease or disorder. These inclusion/exclusion criteria will minimize any potential confounding variables, thereby increasing the internal validity of the proposed studies. Any person matching the inclusion criteria of the study, regardless of race or gender, will be recruited to participate.

Specific Aim 2. We will recruit 15 sprinters; ten with unilateral transtbial amputations and five with bilateral transtibial amputations that currently use and have at least one year of experience with sprint-running RSPs. Subjects will be between 18-55 years old and have no current problems with their prosthesis or residual limb. There will be no restrictions on sex, race, or ethnicity for inclusion. Subjects will be at a K4 Medicare Functional Classification Level, which is defined as a person who has the ability or potential for prosthetic ambulation that exceeds basic ambulation skills, exhibiting high impact, stress, or energy levels. Subjects will have no known cardiovascular, pulmonary, or neurological disease or disorder. These inclusion/exclusion criteria will minimize any potential confounding variables, thereby increasing the internal validity of the proposed studies. Any person matching the inclusion criteria of the study, regardless of race or gender, will be recruited to participate.

[figure not shown]

Figure 2. Overview of the experimental design. We will vary distance-running RSP (*Specific Aim 1*) and sprint-running RSP (*Specific Aim 2*) stiffness (k) and height (h) to create guidelines for prosthetic prescription.

C. Study Design and Research Methods

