The study will be a repeated-measures design. We will calculate subject and group averages for each condition from data normalized to a gait cycle. The data analyzed will include: leg stiffness, peak vertical and horizontal ground reaction forces, stance time, leg swing time, metabolic costs, top speed, peak socket pressure, and maximum socket motion. We will use repeated measures analysis of variance (ANOVA) to compare each variable across all conditions. Any significant differences will be further analyzed with either a Tukey HSD or Newman-Keuls follow-up procedure. In the case of an unequal number of subjects, we will use a Sheffe follow-up procedure. We will use p < 0.05 as a criterion for determining statistical significance. All statistical analyses will be performed with JMPIN software (JMPIN, SAS Institute, Cary, NC).

Specific Aim 1. Subjects will complete six experimental sessions at the University of Colorado Locomotion Lab; each session on a separate day and requiring approximately two hours of time. During each experimental session, subjects will run at two speeds, the speed required for their age/sex 50th percentile PFT (Physical Fitness Test) 2 mile run and a standard speed of 3 m/s on a force measuring treadmill while we measure their ground reaction forces, metabolic demand, socket pressures, and socket pistoning. Subjects will run with three different brands (Ossur,

Ottobock, and Freedom Innovations) of distance-running RSPs with three different stiffnesses at one height and three different heights at one stiffness of each brand, a total of five or more different conditions per brand at two speeds. Individual trials will be five minutes long with at least 2 minutes rest between trials.

Day DR0: Subjects will be asked to give informed written consent and then will be fit and aligned by a certified prosthetist with three different distance-running RSP brands, one from each company. We will measure each subject's height, weight, and limb segment lengths. Then, we will select an RSP stiffness category based on the subject's weight and manufacturer's recommendation. An appropriate RSP height for each subject will be chosen according to conventional practice. Our prosthetist will ensure that the prosthetic fit and alignment are adequate. Then, subjects will have time to accommodate to treadmill running with each distance-running RSP.

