Day DR1: We will first vary the distance-running RSP stiffness (k) while keeping height (h) at the traditionally recommended level. Subjects will use an RSP with the manufacturer's recommended stiffness category based on their weight, an RSP that is one category softer (k-) and an RSP that is one category stiffer (k+) than the manufacturer's recommended stiffness. We will measure ground reaction forces, metabolic demand, socket pressures, and socket pistoning while subjects run at the speed required for their age/sex 50th percentile PFT (Physical Fitness Test) 2 mile run and at 3 m/s, a total of six trials. If the data warrant it, we may add an additional stiffness category to further fine tune the optimal stiffness. The optimal stiffness (k_{opt}) distance-running RSP will be the RSP that minimizes metabolic cost. This RSP stiffness will be used for Day DR2.

 $\underline{\text{Day DR2:}}$ We will keep RSP stiffness constant (k_{opt}) and vary the distance-running RSP height (h). Subjects will have used an RSP with an optimal stiffness (k_{opt}) at the recommended height (h_R) on day Day DR1. On Day DR2, they will also use and RSP with an optimal stiffness (k_{opt}) that is 2 cm shorter (h-), and 2 cm taller (h+). We will measure ground reaction forces, metabolic demand, socket pressures, and socket pistoning while they run at their PTF speed and at 3 m/s; a total of four trials. If the data warrant it, we may further fine tune RSP height in 1 cm increments. We will analyze the results of DR2 to identify the optimal height (h_{opt}) for each subject for one brand of a distance-running RSP.

Days DR3 and DR5: We will repeat the trials of Day DR1 and vary stiffness (k) for a different distance-running RSP brand. We will analyze the results of Days DR3 and DR5 to identify the optimal RSP stiffness (k_{opt}) to be used for Days DR4 and DR6.

Days DR4 and DR6: We will repeat the trials of Day DR2 and vary height (h) for a different distance-running RSP brand. We will analyze the results of Days DR4 and DR6 to identify the optimal height (hoot) for each subject using the respective brand of a distance-running RSP.

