Day SR0: Subjects will be asked to give informed written consent and then will be fit and aligned by a certified prosthetist with three different sprint-running RSP brands, one from each company. We will measure each subject's height, weight, and limb segment lengths. Then, we will select an RSP stiffness category based on the subject's weight and manufacturer's recommendation. An appropriate RSP height for each subject will be chosen according to conventional practice. Our prosthetist will ensure that the prosthetic fit and alignment are adequate. Then, subjects will have time to accommodate to treadmill running and sprinting with each sprintrunning RSP over a range of speeds.

Day SR1: We will first vary the sprint-running RSP stiffness (k) while keeping height (h) at the recommended level. Subjects will use an RSP with the manufacturer's recommended stiffness category based on their weight, an RSP that is one category softer (k-) and an RSP that is one category stiffer (k+) than the manufacturer's recommended stiffness. We will measure ground reaction forces, top speed, socket pressures, and socket pistoning while subjects run and sprint over a range of speeds from 3 m/s up to their top speed. If the data warrant it, we may add an additional stiffness category to further fine tune the optimal stiffness. The optimal stiffness (k_{opt}) sprint-running RSP will be the RSP that maximizes top speed. This RSP stiffness will be used for Day SR2.

Day SR2: We will keep RSP stiffness constant (k_{opt}) and vary the sprint-running RSP height (h). Subjects will have used an RSP with an optimal stiffness (k_{opt}) at the recommended height (h_R) on day Day SR1. On Day SR2, they will also use and RSP with an optimal stiffness (k_{opt}) that is 2 cm shorter (h-), and 2 cm taller (h+). We will measure ground reaction forces, top speed, socket pressures, and socket pistoning while they run across a range of speeds from 3 m/s up to their top speed. If the data warrant it, we may further fine tune RSP height in 1 cm increments. We will analyze the results of SR2 to identify the optimal height (h_{opt}) for each subject for one brand of a sprint-running RSP

Days SR3 and SR5: We will repeat the trials of Day SR1 and vary stiffness (k) for a different sprint-running RSP brand. We will analyze the results of Days SR3 and SR5 to identify the optimal RSP stiffness (k_{opt}) to be used for Days SR4 and SR6.

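### The ANOVA across all conditions has no valid contrast of height against the recommended height, because the height cells are run at each subject's own chosen stiffness and the stiffness cells at fixed categories

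*Combined protocol and SAP*

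**What the plan says.** Section IV.C (Study Design and Research Methods) gives one analysis for every variable: "We will use repeated measures analysis of variance (ANOVA) to compare each variable across all conditions". Significant results go to Tukey HSD or Newman-Keuls (Scheffé if numbers are unequal), and "We will use p < 0.05 as a criterion for determining statistical significance". No factor structure is given, nor any coding of the conditions. Section IV.F (Data Analysis Plan) deals only with records and confidentiality.

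The conditions are "three different stiffnesses at one height and three different heights at one stiffness of each brand", which for Aim 1 is "a total of five or more different conditions per brand at two speeds". The sequence is the same in both aims:

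- **Days DR1 and SR1.** Recommended stiffness (k_R), one category softer (k−) and one stiffer (k+), all at the recommended height h_R. The subject's k_opt is the stiffness with the lowest metabolic cost (Aim 1) or the highest top speed (Aim 2).
- **Day DR2.** "We will keep RSP stiffness constant (k_{opt}) and vary the distance-running RSP height (h". Day SR2 is worded alike for sprinting. Only the shorter (h−) and taller (h+) settings are run. The h_R value at k_opt is the one already recorded on DR1 or SR1.

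Section IV.E expects the optimal stiffness to be softer or stiffer than the recommendation in some subjects, so k_opt is expected to vary.

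**The concern.** The columns of an ANOVA over all conditions do not differ in one thing at a time. A stiffness column holds one category for everyone. A height column holds whichever stiffness suited each subject best. If optimal stiffness truly differs between subjects, both height columns carry the gain from individual stiffness. They can then look better than a fixed-stiffness column when height does nothing, and the same offset can hide a real harm from changing height.

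The obvious alternative is to compare three heights within subject and take the DR1 or SR1 winner as h_R. That has its own problem. The winner was picked because its observed value was best, so for the selecting outcome it is flattered by chance and the other heights look worse. The plan does not say which analysis is meant. At stake is the group statement about height in both aims.

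**Working it through.** **Cell count, from section IV.C.** Conditions per brand: 3 stiffnesses + 3 heights − 1 shared cell = 5, which matches the plan. DR1 has 3 × 2 speeds = 6 trials and DR2 has 2 × 2 = 4. Both match, and the second confirms that h_R is not re-run on DR2.

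**Pairs.** Five columns give 5 × 4 / 2 = 10 pairs.

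- Stiffness only (among k−, k_R, k+): 3.
- Height only (h− against h+): 1.
- Height column against stiffness column: 2 × 3 = 6. In these, height changes for everyone and stiffness changes for every subject whose k_opt is not that column's category.

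No column is k_opt at h_R for all subjects.

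**Size in percent.** The documents give no SD or effect size. Assumed: 15 subjects, one brand, within-subject SD 2% of the outcome, cost rising by a fixed penalty per category away from the subject's true optimum, optima spread evenly over the three categories, k_opt taken as the observed best, and no height effect. The five-column analysis is a subject-blocked ANOVA with Tukey, q(5, 56) = 3.99. Results are by simulation.

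| Penalty per category | Five columns: a height cell beats some stiffness cell | Five columns: a height cell beats the recommended cell | Three heights, reused h_R: h−/h+ look worse by | Three heights, reused h_R: false rejection |
|---|---|---|---|---|
| 0% | no bias | no bias | 1.7% | 71% |
| 2% | 28% | 3% | 1.2% | 36% |
| 3% | 70% | 9% | 0.8% | 18% |
| 4% | 92% | 19% | 0.5% | about 10% |

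Two checks by hand:

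- At a 3% penalty with perfect selection, the k_R column would sit (3 + 0 + 3)/3 = 2.0% above the optimum, and k− or k+ (0 + 3 + 6)/3 = 3.0%. Selection from noisy data is imperfect, and the simulated gaps are 1.4% and 2.4%.
- With no stiffness effect, the reused winner is the minimum of three equal normals, expected at −0.846 SD. 0.846 × 2% = 1.7%, as in the table.

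**The same under a different model.** Let each subject's three stiffness effects vary with SD τ, in units of the error SD, with no average stiffness effect and no height effect. Then:

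- five columns: height minus k_R column = −0.846 τ²/√(τ² + 1)
- reused reference: h−/h+ minus h_R = +0.846/√(τ² + 1)

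At τ = 1 these are −0.60 and +0.60. At τ = 2 they are −1.51 and +0.38. At τ = 0 they are 0 and +0.85. In simulation at τ = 0, 0.5, 1 and 2, Tukey flags at least one height-against-stiffness pair in 3.5%, 5.6%, 23% and 71% of trials. The three-height ANOVA with the reused cell rejects in 71%, 58%, 37% and 16%.

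**With a fresh reference.** If k_opt at h_R is measured again alongside h− and h+ and only those three cells are compared, bias is about zero and rejection about 5% under both models. For an outcome not used to choose k_opt, the reused run also gives about 5%, provided its errors are independent of those of the selecting outcome.

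**The case against.** The plan gives one generic sentence. It does not commit to a five-column model, and the height series is described as three heights at one stiffness. Separate stiffness and height ANOVAs are therefore just as consistent with the text. This stands: what the documents show is an unspecified analysis, not a declared wrong one. It does not rescue the plan, because for metabolic cost and top speed the second reading is biased too.

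Four stronger conclusions are tempting, and none is supported:

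- *That h_R has nothing to be compared with.* Every subject has a k_opt run at h_R from DR1 or SR1. What is missing is a common column and, for the selecting outcomes, an unselected measurement.
- *That the gain from individual stiffness will be reported as a height benefit.* This needs the five-column reading and true between-subject differences in optimal stiffness. The other reading pushes the opposite way. The large rates also count wins over any stiffness cell; wins over the recommended cell are about 3–19%.
- *That rewording alone cures it.* With existing data only, the split height analysis still uses the selected winner for metabolic cost and top speed.
- *That the height half of both aims fails.* Hypotheses 1 and 2 concern the optimum for each subject. Section IV.C identifies k_opt and h_opt subject by subject from the session results, not from the group ANOVA.

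**Conclusion.** The point holds for the group inference on height. The cell structure comes straight from the documents: a five-column ANOVA has no valid contrast of height with recommended height, and 6 of its 10 pairs are mixed. Neither available reading gives a sound height test for metabolic cost or top speed, and the two err in opposite directions.

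The sizes rest on assumptions that the documents do not supply: SD 2%, penalties of 0–4% per category, evenly spread optima, normal errors. Within them, the five-column bias is zero without a stiffness effect and grows with it. The reused-reference bias is greatest without a stiffness effect (1.7%, 71% false rejection) and shrinks to 0.5% and about 10% at a 4% penalty. The individual choice of prosthesis is not shown to be affected by the ANOVA.

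**What to change.** 1. Replace the all-conditions ANOVA by two analyses per variable: stiffness (k−, k_R, k+ at h_R) and height (h−, h_R, h+ at the subject's own k_opt). State that no follow-up test crosses the two sets.
2. For outcomes not used to choose k_opt, the DR1 or SR1 run at k_opt and h_R may serve as the height reference. State the assumption that their errors are independent of the selecting outcome, and note that this run is from a different day.
3. For metabolic cost and top speed, repeat the k_opt, h_R measurement in the height session and use only the repeat as reference. If it is not repeated, report the contrast with h_R for these two outcomes as biased by selection and test only h− against h+.

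Items 1 and 2 are changes of wording. Item 3 takes the Aim 1 height session from 4 to 3 × 2 = 6 trials, equal to DR1. It takes the Aim 2 height session from two series to three, the daily maximum in section IV.C. Over three brands that is 3 × 2 = 6 extra five-minute trials per runner, or 3 extra series per sprinter. Section IV.E says Days 2, 4 and 6 have room for an additional condition. The cost is that this room is otherwise kept for fine-tuning stiffness and height, so fine-tuning may then need the extra day that section IV.E already allows for.

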Specific Aim 2. Subjects will complete six experimental sessions at the University of Colorado Locomotion Laboratory; each session on a separate day and requiring approximately two hours of time. During each experimental session, subjects will run and sprint over a range of speeds, from 3 m/s up to top speed on a force measuring treadmill while we measure their ground reaction forces, socket pressures, and socket pistoning. Subjects will run with three different brands (Ossur, Ottobock, and Freedom Innovations) of sprint-running RSPs with at least three different stiffnesses at one height and three different heights at one stiffness of each brand, a total of five or more different conditions per brand. Individual trials at each speed will be approximately 15-30 seconds long with at least 2 minutes rest between trials.

A safety harness attached to the ceiling above the treadmill and handrails beside the treadmill will be used during all running/sprinting trials to ensure subjects' safety. Each running trial will consist of at least 10 strides. To begin each trial, subjects will lower themselves from the handrails on to the moving treadmill belt. For each prosthetic stiffness and height condition, subjects will start a series of trials at 3 m/s, each subsequent trial will be incremented by 1 m/s until subjects approach their top speed, and then smaller speed increments will be employed until subjects reach their top speed. *Top speed* will be determined when subjects put forth maximal effort but cannot maintain their position on the treadmill for ten strides (Weyand, Sternlight, Bellizzi, & Wright, 2000). Subjects will be given as much time between trials as needed to recover fully (at least 2 minutes). At least seven trials will be performed by each subject for each prosthetic condition (e.g. 3, 4, 5, 6,

7, 7.3, 7.5 m/s) and a maximum of three series of trials will be performed each day. Our results will allow us to determine the optimal RSP mechanical stiffness (k_{opt}) and height (h_{opt}) for each person. The optimal sprint-running (SR) RSP will be the prosthesis that maximizes top speed.

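### Newman-Keuls is allowed as a free alternative to Tukey HSD; with four or more conditions compared together its familywise error can reach about 9–10% within one brand

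*Combined protocol and SAP*

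**What the plan says.** The analysis paragraph opening section IV.C states: "We will use repeated measures analysis of variance (ANOVA) to compare each variable across all conditions". It continues: "Any significant differences will be further analyzed with either a Tukey HSD or Newman-Keuls follow-up procedure". For unbalanced data it adds: "In the case of an unequal number of subjects, we will use a Sheffe follow-up procedure". The threshold is given once: "We will use p < 0.05 as a criterion for determining statistical significance". It is not said whether 0.05 applies to each comparison, each variable, each brand or the whole study. Section IV.F, although titled Data Analysis Plan, deals with records and data security and adds nothing here.

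On the number of conditions, Specific Aim 1 describes "a total of five or more different conditions per brand at two speeds", with three brands. Specific Aim 2 has "at least three different stiffnesses at one height and three different heights at one stiffness of each brand". The daily schedule first varies stiffness over three levels at one height, then height over three levels at each subject's best stiffness. It leaves room for more levels: "If the data warrant it, we may add an additional stiffness category to further fine tune the optimal stiffness". Section IV.B sets 15 subjects per aim, ten unilateral and five bilateral.

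**The concern.** The two procedures offered as equals have different error control. Under sphericity, Tukey HSD holds the familywise rate whatever the true means are. Newman-Keuls does so only for some patterns of means. It also never declares fewer pairs different than Tukey does, so a choice left open until the data are in can favour the procedure that finds more.

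At stake are the group-level statements about which stiffnesses, heights or brands differ. These would feed the prescription algorithms announced in section IV.G. A false difference between two settings could enter that guidance with a nominal 5% label when the real rate is about twice as high.

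**Working it through.** **Inputs.** From the documents: threshold 0.05; three levels per stiffness or height day; four if a stiffness category is added; five or more per brand; three brands; n = 15 per aim (10 unilateral, 5 bilateral). Assumed, because the plan gives neither means nor SDs: normal errors, sphericity, and gaps between clusters of equal means expressed in residual SDs. The plan states no familywise figure to reproduce.

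**Why the number of conditions matters.** Newman-Keuls compares a range of p ordered means with the studentized-range value for p means; Tukey uses the value for all k. Once the wide ranges are rejected, each cluster of equal means is tested by Newman-Keuls at its own 5%. With m well-separated clusters the familywise error approaches 1 − 0.95^m.

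- One cluster (m = 1): 5%.
- Two clusters (m = 2): 1 − 0.95² = 9.75%.

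Two clusters of at least two means need four conditions. With three conditions only one such cluster can exist, so there is nothing to accumulate.

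**Simulation.** Error mean square on (k − 1)(n − 1) df, for example 4 × 14 = 56 for k = 5 and n = 15. Follow-up tests count only if the omnibus F is significant at 0.05. An error is any rejected pair with equal true means. Ranges cover separate runs.

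Familywise error at n = 15:

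| Pattern | Newman-Keuls, 0.5 SD | 1 SD | 2 SD | Tukey, these gaps |
|---|---|---|---|---|
| 3 conditions, 2+1 | 3.7% | 4.7% | 5.0–5.2% | about 2% |
| 4 conditions, 2+2 | 5.4% | 9.0–9.4% | 9.7% | about 2% |
| 5 conditions, 3+2 | 4.7–5.6% | 8.7–9.6% | 9.4–10.6% | 2.3–2.6% |
| 5 conditions, 2+2+1 | 4.3–4.6% | 8.7–9.6% | 9.4–10.0% | 1.3–1.5% |

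Values slightly above 9.75% are simulation noise. At 0.75 SD the five-condition patterns give 7.5%. With all means equal, Newman-Keuls gives 4.4–4.5% (k = 3) and 3.7–4.1% (k = 5). Five conditions as 4+1 give at most 5.1%.

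**Smaller groups.** At n = 10 the two-cluster figures are 7.7–8.5% at 1 SD and 9.1–9.7% at 2 SD, with Tukey at most 2.7%. At n = 5 they are 5.0–6.3% at 1 SD and 9.3–9.9% at 2 SD. The gap at which inflation appears therefore grows as n falls.

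**Does the F test protect?** Only when all means are equal. For 3+2 at gaps of 0.5, 0.75 and 1 SD it is significant in 33, 68 and 92% of runs.

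**Across brands.** If 0.05 is applied within each of three brands, the ceiling is 1 − 0.95³ = 14.3%, whichever valid procedure is used. With Tukey after the F test (about 4.0% per brand when its five means are equal) the expected figure is 1 − 0.96³ = 11.5%; simulation gave 11.4–12.7%. One Tukey family over all 15 conditions gives about 2% when each brand is a cluster of equal means.

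**Sphericity.** Tukey depends on it. With all means equal and one condition assumed to have twice the SD of the others, Tukey after the F test gives 5.5% (k = 3) and 6.2% (k = 5) at n = 15, and 5.9% and 7.1% at n = 10. With three times the SD it gives 6.4% and 8.4%. Holm-adjusted paired t tests stay at 3.5–4.7% in all these cases. A pre-test does not rescue Tukey: with Mauchly's test at 0.05 (an assumed rule), n = 15 and the twofold SD, the violation is detected in only 38% (k = 3) and 44% (k = 5) of runs, and the two-stage error is 6.1% and 5.8%.

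**Scheffé against Tukey, n = 15.** Multipliers √((k − 1)F) against q/√2: 2.585 against 2.474 for k = 3 (ratio 1.04) and 3.185 against 2.819 for k = 5 (ratio 1.13). Where Tukey has 80% power for one pair, Scheffé has 77% and 69%.

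**The case against.** The best defence is that the design describes three-level steps, for which Newman-Keuls is sound. Because the best stiffness is chosen per subject, the reference cell of the height comparison is a different stiffness for different people, so a pooled five-level ANOVA fits awkwardly. The plan claims no familywise control and names no confirmatory endpoint. Clusters of exactly equal means 1 SD apart are a construction, and no SD is given to say whether they are realistic.

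Most of this stands as a limit on the point. It does not remove it: the text says all conditions, nowhere restricts the ANOVA to three levels, and allows an added stiffness category. Four levels are enough.

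Three stronger readings are tempting, and the documents do not support them.

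- **That the trial faces a 12–15% error over three brand clusters, which Tukey would cure.** The text does not say whether brands share one ANOVA. The pattern requires stiffness and height to have no effect within any brand, contrary to the premise of Hypotheses 1 and 2. Tukey applied brand by brand has the same 14.3% ceiling.
- **That Scheffé is a mistake.** It is valid for every contrast and is only wider than pairwise questions need.
- **That subjects' optimal prostheses are put in doubt.** Section IV.C selects them by lowest metabolic cost or highest top speed, without these tests.

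**Conclusion.** The point holds as a limited one. The plan permits, on equal terms and with no rule for choosing, a procedure that fails to hold 5% in part of the range of analyses its wording allows. At n = 15 the rate is roughly doubled within a brand when four or more conditions are compared together and two clusters of equal means lie about 1 residual SD or more apart; smaller groups need a wider gap. Outside those conditions there is no inflation.

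The size rests on assumed gaps, normal errors and sphericity. A reader might infer that the trial's group findings will in fact be inflated; without an SD or effect size the documents cannot show that. The change is still worth making, because the replacement holds its level in every pattern examined under sphericity and costs almost nothing.

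**What to change.** In the analysis paragraph of section IV.C:

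1. Delete Newman-Keuls. Name one procedure before the data are seen: Tukey HSD, or Holm-adjusted paired contrasts throughout. The Holm option does not rely on sphericity, so it needs no sphericity pre-test and no data-dependent switch.
2. State the family to which 0.05 applies, for instance all pairwise comparisons of one variable within one brand and speed. If the family is one brand, state that error across the three brands can reach about 14%. If brands enter one ANOVA, use a single Tukey or Holm family over all those conditions.
3. If only the three-level stiffness and height comparisons are intended, say so, and say how an added level is handled.
4. Optional: for unequal numbers, replace Scheffé with Tukey-Kramer or Holm. The power gain is small with three conditions and larger with five. With 3 of 15 subjects each assumed to miss one condition at random, power at k = 5 and a 1.34 SD difference was 76.7% (Tukey-Kramer), 76.1% (Holm) and 64.7% (Scheffé). Conditions added because of a subject's own results are not missing at random in that sense, and none of these procedures corrects for that.

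The cost is wording only; data collection is unchanged. The downside is fewer nominally significant pairs than Newman-Keuls would give. Multiplicity across the nine listed variables is a separate matter that this change leaves open.
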